Setting: Screening, baseline, outcome testing and intervention meetings will be conducted at the Sarah W. Stedman Center for Nutritional Studies on the Center for Living Research and Wellness campus at Duke University. Diet and exercise classes will be offered virtually via WebEx or in person at the Center for Living campus. Anthropometrics, functions tests, and blood collection will take place in the Clinical Research Unit there or may be conducted virtually if needed. The Isokinetic knee extension peak torque testing and BodPod body composition measurements will be done in the Sports Sciences Institute, which is adjacent to the Stedman Building. The thigh CT scans will be conducted in Radiology at the Veterans Affairs Medical Center in Durham.

We will enroll participants until we reach a total of 112 study completers. We anticipate enrolling approximately 160, allowing for a 30% dropout rate.

Study Arms:

- **Arm 1: WL-Control (n=56 completers)**
10%* WL diet with 0.8 g protein/kg body wt/day
- **Arm 2: WL-Pro (n=56 completers)**
10%* WL diet 1.4 g protein/kg body wt/day; \geq 30g high quality protein per meal

**Participants enrolled after 10/1/2023 will participate in a shortened study period of 3 months, with only 0 and 3 month assessments for most measures, as noted in the added footnotes below. Their weight loss prescription will be targeted to an expectation of at least 5-10% loss of body weight.*

Measurements:

After the participant has been consented and HIPAA Authorization forms have been signed, screening and baseline assessments will be conducted:

Screening process:

Screening Visit : Consent; confirm BMI ≥ 30 kg/m², confirmed SPPB score of 4-11, confirmed fasting plasma glucose ≥ 95 and < 126 mg/Dl or A1c between 5.7-6.4 (will be confirmed with LapCorp results), and confirmed Mini-Cog score ≥ 3 (if less than 3, confirm participant can conduct all ADLs).

Upon the completion of all baseline assessments (see below), the study biostatistician will then use permuted-block randomization to assign participants to WL-Control or WL-Protein groups. The following variables will be blocked in this order: 1) Race (white versus non-white, 2) Couple/Single status. An equal number of participants will be randomized across the two arms to end up with N=84 (42 black and 42 white) in each arm.

Measures and Data Collection Points

Primary outcome: Physical function (SPPB)

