Aim 2: To determine the effect size for subsequent studies of virtual interventions for high risk obese older Veterans with physical function as the outcome of primary interest (virtual SPPB). Outcomes will also be collected for the secondary measures of weight loss, physical function, insulin resistance (Glycated Hemoglobin; Hb A1c), cognitive function, and quality of life.

Exploratory Aim 3 (given restoration of full in-person clinical research testing visits):

To determine the effect size for subsequent studies of virtual interventions for high risk obese older Veterans with regards to the primary outcome of (in-person) SPPB and the in-person secondary outcomes of insulin sensitivity and muscle quality (thigh CT scan, knee extensor peak torque).

Achievement of this Aim would allow comparison of the high-risk participants to the participants that do not have 2 or more age and/or COVID-19 related social isolation risk factors (Table 2).

Significance with regard to COVID-19 impact on Veterans:

The COVID-19 pandemic and resulting social isolation is worsening health conditions in all older adults, including Veterans. Obesity is promoted by overeating due to increased stress and/or reduced access to healthy food options. In our recent recruitments for obesity trials, many of our participants are reporting experiencing a marked weight gain since the pandemic came to our community. Deterioration of physical fitness and function are also being documented.⁵⁷ In addition to exacerbating chronic conditions like type 2 diabetes and hypertension, obesity increases the risk of serious complications and death if a COVID-19 infection occurs. There is a critical and time-dependent need to develop strategies to reverse the trend towards obesity-related physical frailty in our vulnerable older Veterans. The proposed research can be initiated quickly because effective remote interventions have already been developed in the parent trial and are ready for use in this study. Another significant point is that the trial also enrolls a substantial proportion of African American Veterans, an important advantage because minority older adults are known to be more vulnerable to COVID-19 complications.⁵⁸

[figure not shown]
Study Design: High risk, obese, male Veterans with prediabetes and SPPB score of 4-11 (out of 12), aged ≥ 55 yrs will be randomized to a higher protein, calorie-restricted diet OR a calorie-restricted diet with RDA level protein in a 6-month trial (Fig. 2).

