This design is a two-armed clinical trial, with replicate measures at three time points: baseline, three, and six months. Since subjects are randomized to either WL-Control or WL-Protein arm, and the groups are presumed equal at baseline, the analysis is straightforward. Following the Good Clinical Practice Guidelines for the analysis of a clinical trial, we will employ mixed models, analyze under an Intent to Treat (ITT) criteria, and control for baseline and assess the impact of Time, Treatment Group and the interaction of these variables on the outcomes. Relative to the usual repeated measures designs, mixed models have several advantages: 1) missing values present no particular difficulties in estimation and the estimates are unbiased as long as the set of variables leading to MAR are estimated, 2) the usual assumption of conditional independence (compound symmetry) used in standard repeated measures need not be made, and 3) the actual times of measurement need not be equivalent across subjects. Controlling for the individual baseline values for the particular outcomes, the trajectories over time and differences in those trajectories will be assessed. Following the statistical principles section from the International Conference on Harmonization, we will select covariates (e.g., age, race, number of comorbidities) for the primary models a priori, but we also will conduct auxiliary sensitivity analyses that evaluate whether potential group imbalances bias the treatment effect estimate. These analyses will be performed using conventional testing for confounding. We note that we have listed numerous measures to be analyzed as outcomes, but have listed only 1 primary outcome (physical function, Aim 1).

For any particular outcome, the general form of the model will be:

$$Y_{it} = \beta_0 + \beta_1(\text{group}) + \beta_2(\text{time}_t) + \beta_3(\text{group} * \text{time}_t) + \beta_4(\text{covariates}) + \epsilon_{it}$$

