Where i is an indicator of person, and time is defined as $t=1, 2$ (measuring month 3, and 6), and the β 's are regression coefficients connecting the predictors to the outcome. For brevity, we list β_4 as a vector of K regression coefficients linking the K covariates to the outcome. As defined, the overall test of the intervention effect will be the joint effect of group and group*time on 2 df (β_1 and β_2) assessing an overall effect of group, and if this group effect is constant over time. If significant, follow-up tests will assess where group differences lie. In particular, we note that if the time by group interaction is rejected, we will test if the groups differ at the end of 6 months (a test of effect at the completion of the intervention). We will carefully examine model assumptions, including the distribution of model residuals, additively, linearity, and influential observations, and will, if necessary, re-parameterize the models or transform the outcomes accordingly.

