Aim 2 and 3: This design is a two-armed feasibility trial, with replicate measures at three time points: baseline, three, and six months. Since subjects are randomized to either HR-WL-Protein or HR-WL-Control, and the groups are presumed equal at baseline, we will employ mixed models, analyze under an Intent to Treat (ITT) criteria, and control for baseline and assess the impact of Time, Treatment Group and the interaction of these variables on the outcomes. Controlling for the individual baseline values for the particular outcomes, the trajectories over time and differences in those trajectories will be assessed. Following the statistical principles section from the International Conference on Harmonization, we will select covariates (e.g., age, race, number of comorbidities) for the primary models a priori, but we also will conduct auxiliary sensitivity analyses that evaluate whether potential group imbalances bias the treatment effect estimate. These analyses will be performed using conventional testing for confounding. As defined, the overall test of the intervention effect will be the joint effect of group and group*time on 2 df assessing an overall effect of group, and if this group effect is constant over time. If significant, follow-up tests will assess where group differences lie. In particular, we note that if the time by group interaction is rejected, we will test if the groups differ at the end of 6 months (a test of effect at the completion of the intervention). We will carefully examine model assumptions, including the distribution of model residuals, additively, linearity, and influential observations, and will, if necessary, re-parameterize the models or transform the outcomes accordingly.

Privacy, Confidentiality, and Information Security

Lists of Data Reviewed and/or Collected for Screening/Recruitment and Conduction of Study:

- Demographics: age, race, gender, weight, height, marital status, education, employment status, living arrangements, socioeconomic and smoking status
- Diagnosis of pre-diabetes
- Mini Cog
- Hand-grip strength
- Weight
- Height
- Physical Function – Short physical performance battery, 6-minute walk, 30 second chair stand, 8 foot up and go
- Physical activity – Actigraph and wear log
- CT-scan of the thigh

- Isokinetic knee extensor peak torque
- Three-day food record
- Protein checklist
- Nutrition Literacy Questionnaire
- Food Security Questionnaire
- Intervention Evaluation Questionnaire

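### The plan does not say whether in-person baselines may be missing at randomisation; if any are, its baseline-covariate model drops those men from that outcome

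*Combined protocol and SAP*

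**What the plan says.** **Randomisation.** Under Design, Screening process, the parent protocol says: "Upon the completion of all baseline assessments (see below), the study biostatistician will then use permuted-block randomization". The measurement table puts thigh CT, isokinetic knee torque, BodPod and SPPB at month 0.

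**In-person testing.** The Setting paragraph allows some remote testing: "Anthropometrics, functions tests, and blood collection will take place in the Clinical Research Unit there or may be conducted virtually if needed". It then lists torque, BodPod and CT separately, with no virtual option. In the supplement, Exploratory Aim 3 (in-person SPPB, insulin sensitivity, and muscle quality from CT and torque) applies "given restoration of full in-person clinical research testing visits". Supplement Aim 2, based on virtual SPPB, carries no such condition. The supplement's measurement table has SPPB and virtual SPPB as separate rows, both at month 0.

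**Analysis.** The plan for parent Aims 1 and 2 will "analyze under an Intent to Treat (ITT) criteria, and control for baseline", and continues: "Controlling for the individual baseline values for the particular outcomes, the trajectories over time and differences in those trajectories will be assessed". The supplement's analysis plan repeats this. In the parent model equation the time index covers months 3 and 6 only. On missing data the plan says that "missing values present no particular difficulties in estimation", and that estimates are unbiased provided the variables behind missingness at random are accounted for. It gives no rule for a missing baseline: no imputation, no indicator, and no model with baseline as a response.

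**The concern.** A likelihood-based mixed model copes with a missing response because the man's other responses still enter the likelihood. It has no such mechanism for a missing covariate: a standard fit removes every row in which the covariate is absent. Month 0 is not a response here, so baseline can enter only as a covariate.

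The supplement opens a route to that situation. If supplement men could not be randomised until every in-person baseline was done, there would be little reason to make only Aim 3 depend on restored visits while Aim 2 goes ahead on virtual SPPB. A man randomised during suspension and tested in person at month 3 or 6 would have values that the model does not use. That sits badly with the intent-to-treat statement. The outcomes exposed are mainly muscle quality (CT and torque) and, for supplement Aim 3, in-person SPPB. Insulin sensitivity is on the same conditional list.

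**Working it through.** **Figures in the plan.** None is in dispute. For SPPB, (2.4 − 0.9)/1.7 = 0.88. A two-sample t calculation with 50 per arm gives 99.2% power at that effect and a detectable difference of 0.566 SD, or 0.962 units (plan: above 99%, 0.57, 0.96). Enrolment is 112/(1 − 0.30) = 160, as stated.

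**Does the model drop these men?** In one simulated data set of 112 men, with all month-3 and month-6 values present and 42 baselines deleted, the baseline-covariate mixed model used 70 men and 140 of 224 rows.

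**Cost in precision.**

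Inputs from the documents: n = 56 completers per arm (Design).

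Assumed, because the documents give none of these: unit variance; month 3–month 6 correlation 0.8; baseline–follow-up correlation r = 0.5, 0.7 or 0.8; a share f of men in each arm without a baseline; all later values observed.

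- Planned model, using only the (1 − f)n men per arm with a baseline: variance of the month-6 arm effect = 2(1 − r²)/[(1 − f)n].
- Alternative model, with baseline as a response and a common mean: variance = 1/[(1 − f)n/(1.8 − 2r²) + fn/1.8] + 0.2/n. Here 1.8 and 0.2 are 1 ± 0.8. With f = 0 this equals 2(1 − r²)/n, the same as the planned model.

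Worked case, f = 0.26 and r = 0.5, so 41.44 men per arm with a baseline and 14.56 without:
- Planned: √[2 × 0.75/41.44] = 0.1903.
- Alternative: √[1/(41.44/1.3 + 14.56/1.8) + 0.2/56] = √[1/39.97 + 0.00357] = 0.1691.
- Ratio: 1.13.

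Standard errors in SD units, planned / alternative:

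| f | r = 0.5 | r = 0.7 | r = 0.8 | Ratio |
|---|---|---|---|---|
| 0% | 0.1637 / 0.1637 | 0.1350 / 0.1350 | 0.1134 / 0.1134 | 1.00 |
| 5% | 0.1679 / 0.1647 | 0.1385 / 0.1365 | 0.1163 / 0.1149 | 1.01–1.02 |
| 10% | 0.1725 / 0.1657 | 0.1423 / 0.1380 | 0.1195 / 0.1165 | 1.03–1.04 |
| 26% | 0.1903 / 0.1691 | 0.1569 / 0.1436 | 0.1318 / 0.1223 | 1.08–1.13 |

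The 26% row is 42/160, the supplement's size over planned enrolment. It is a reference point, not an estimate of how many baselines are missing.

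**The case against.** The strongest reply is that the path may be empty. The randomisation rule requires all baseline assessments, and the data-acquisition section gives the same order of visits: blood screen, then function, body composition and torque, then CT. The supplement lists muscle quality at months 0, 3 and 6, so Exploratory Aim 3 may be meant only for men who can be tested at all three. If so, f = 0 and nothing is lost. This stands as a reason to word the point conditionally. It does not settle the matter, because the supplement never says that randomisation waits for in-person tests.

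Four stronger readings are tempting, and the documents do not support them:

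- *Men randomised during suspension have no CT, torque or BodPod baseline.* No section says so. BodPod is less clear than CT and torque: it has no virtual option, but the supplement puts it under the unconditional Aim 2.
- *The 42 supplement men are the number affected, or an upper limit.* They are defined by isolation risk factors, and suspended visits would affect other men equally. The arm descriptions also call them completers, so the matching share could be 42/112 = 37.5%. At a common correlation of 0.7 that gives 0.171 against 0.148, a ratio of 1.16.
- *The treatment estimate is biased.* If a baseline is missing because of calendar time, before assignment, its loss does not depend on arm.
- *The primary analysis loses men.* Function tests may be done virtually, so this route does not remove men from the parent SPPB analysis.

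The missing-data sentence is also a general comparison with older repeated-measures methods, and it carries a missing-at-random condition. It is incomplete for this case rather than wrong in general.

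**Conclusion.** The point holds conditionally. The randomisation rule and the supplement's Exploratory Aim 3 must be reconciled. If any man is randomised without a baseline for an in-person outcome, the model as written excludes him from that outcome despite measured later values, and the plan's assurance about missing values does not cover him.

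The cost is mainly precision and intent-to-treat coverage for the in-person secondary outcomes of parent Aim 2 and for exploratory supplement Aim 3. The parent primary SPPB analysis and the power statement are not shown to be affected.

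The size depends on a count that the documents do not give: nothing if no baseline is missing, negligible at 5%, and at 26% between 14% and 21% of the variance avoidable (1 − 1/1.078² and 1 − 1/1.125²). These figures rest on the assumed correlations and on every man having a month-6 value, which men enrolled after 10/1/2023 will not have.

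**What to change.** 1. State which baseline assessments must be complete before randomisation and which may be missing, so that the Screening process rule and the supplement's Exploratory Aim 3 agree. Report how many men in each arm lack each in-person baseline.
2. In the parent and supplement analysis plans, fit months 0, 3 and 6 as responses, with one baseline mean common to both arms and arm-by-time terms at months 3 and 6 (constrained longitudinal model). Every man with any measured value then contributes. With no baseline missing, this gives essentially the same estimate and the same standard error as the planned adjustment. Prespecified imputation of the baseline covariate is an acceptable alternative.
3. Limit the missing-data sentence to missing responses, and add one on missing baselines.

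The cost is a few sentences and a change of SAS code. No visits or participants are added.

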Power Estimate: The sample size of $n = 84$ per group is based directly on our findings in the MEASUR-UP study, which used the same diet treatments, study population, and primary outcome as in the present Aim 1. In MEASUR-UP, the SPPB score for WL-Pro changed by +2.4 units over the course of the study, while the WL-Control group experienced an increase of +0.9 units. The pooled standard deviation of these changes is 1.7. Thus, the MEASUR-UP study observed a standardized difference of $0.88 = (2.4 - 0.9)/1.7$. Differences of this magnitude have been labeled as 'large' in the power analysis literature. Assuming equivalent effect sizes observed in the MEASUR-UP study, an overall sample size of 100 (evenly divided between groups), and a Type-I error rate of 0.05 (two tailed), the power of our design is greater than 99% to declare significance for the effect size observed in the pilot. At 80% power, this design is powered to detect a difference in change scores in the SPPB of 0.96, or a standardized difference of 0.57.

Analysis Plan for the supplemental protocol:

Aim 1: Feasibility-Recruitment capability: Proportion of participants recruited will be calculated as the number of participants deemed potentially eligible and contacted for enrollment divided by the total number of

participants enrolled. Feasibility of recruitment hypothesis: ≥35% of participants approached for recruitment will agree to participate

Feasibility-Retention: Retention proportion retention will be computed by dividing the number of retained subjects at the end of the intervention by the total number randomized into the study.

Retention hypothesis: ≥80% of participants will remain in the study for the duration of the trial

We will calculate the rate of retention and its respective confidence intervals overall and by group. While non-powerful, we will assess if these rates differ by chi-square test of proportion and Poisson regression respectively. In a series of sensitivity tests, we will assess if retention overall was impacted by demographic and high risk variables.

Feasibility-Intervention Tools: Records of intervention tools and time spent to administer them will be used for post-study analysis of intervention tool effectiveness.

Acceptability-Satisfaction: participant satisfaction of intervention delivery, overall experience, and outcomes will be assessed using a Likert scale and open-ended questions.

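### Does the wrong subscript on the primary joint test (β1 and β2 instead of β1 and β3) put the primary analysis at risk?

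*Combined protocol and SAP*

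**What the plan says.** The relevant text is in the combined protocol and SAP, under Analysis Plan for the parent protocol (Aims 1 and 2).

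- **The model.** The right-hand side includes "\beta_1(\text{group}) + \beta_2(\text{time}_t) + \beta_3(\text{group} * \text{time}_t"). So β1 belongs to group, β2 to time and β3 to group-by-time, with β4 standing for the covariates. Time takes two values, months 3 and 6.
- **The overall test.** It is defined in words and then labelled: "the overall test of the intervention effect will be the joint effect of group and group*time on 2 df (β_1 and β_2").
- **Its purpose.** The sentence continues: "assessing an overall effect of group, and if this group effect is constant over time".
- **The aim of the modelling.** After adjustment for baseline, "the trajectories over time and differences in those trajectories will be assessed".
- **The supplemental plan.** Analysis Plan for the supplemental protocol, Aims 2 and 3, gives the same test without symbols: "the joint effect of group and group*time on 2 df assessing an overall effect of group".

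**The concern.** The sentence defines the operative test for the only primary outcome, the SPPB. The same model form is offered for every other outcome, and the Aim 3 plan builds on it. Read by its symbols alone, the test would be of β1 = β2 = 0. That drops the interaction and puts a time slope in its place: the reference arm's slope under 0/1 group coding, or the mean of the two arms' slopes under ±0.5 coding. Such a test could reject when the diets do not differ, simply because both arms improve between month 3 and month 6. Shared improvement is plausible, since both arms receive calorie restriction and exercise, and the Power Estimate section reports that the control arm of the earlier study gained 0.9 units. A degrees-of-freedom check would not expose the slip, because both pairs of coefficients give 2 df.

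**Working it through.** **1. The plan's own figures.** The Power Estimate does not depend on the label. Its inputs are 50 per arm, a difference of 2.4 − 0.9 = 1.5 and an SD of 1.7.

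- Standardized difference: 1.5/1.7 = 0.88.
- Power, normal approximation: Φ(0.882 × √(50/2) − 1.96) = Φ(2.45) = 0.993. A t-test gives 0.992. The plan says above 99%.
- Detectable difference at 80% power: (1.96 + 0.84) × √(2/50) = 0.56 SD, or 0.95 units. A t-test gives 0.566 SD, or 0.96 units. The plan says 0.57 and 0.96.

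These reproduce and do not change with the subscript.

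**2. Words against symbols.**

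| Source | Terms tested | Coefficients in the plan's equation |
|---|---|---|
| Overall test, words | group, group-by-time | β1, β3 |
| Overall test, label | group, time | β1, β2 |
| Stated purpose: is the group effect constant over time? | needs group-by-time | β3 |
| Follow-up at 6 months, conditional on the interaction | needs group-by-time | β3 |
| Supplemental plan, no symbols | group, group-by-time | β1, β3 |

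Only the parenthesis points to β2.

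**3. What literal coding would do.** This is an illustration only.

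From the documents: 56 completers per arm (Study Arms). The SD of 1.7 is given only for SPPB change in the earlier study: "The pooled standard deviation of these changes is 1.7".

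Assumed: SD 1.7 at each visit, correlation ρ = 0.6 between visits, no covariates, every completer measured at both visits, no diet effect, and a gain d from month 3 to month 6 shared by both arms.

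Let s = 1.7²/56 = 0.0516. With t = 1, 2:

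- Var(β1) = 2(5 − 4ρ)s = 5.2s under any coding with the two groups one unit apart.
- The noncentrality for (β1, β2) is d² / [Var(β2) − Cov(β1, β2)²/Var(β1)].

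| Group coding | Var(β2) | Cov(β1, β2) | Bracket | Noncentrality, d = 0.30 |
|---|---|---|---|---|
| 1/2 | 4.0s | 3.6s | 1.508s = 0.0778 | 0.09/0.0778 = 1.16 |
| 0/1 | 0.8s | 1.2s | 0.523s = 0.0270 | 0.09/0.0270 = 3.33 |
| ±0.5 | 0.4s | 0 | 0.400s = 0.0206 | 0.09/0.0206 = 4.36 |

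The rejection rate is the probability that a noncentral chi-square on 2 df exceeds 5.99:

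| Shared gain d | 1/2 | 0/1 | ±0.5 | (β1, β3), any coding |
|---|---|---|---|---|
| 0.05 | 5% | 6% | 6% | 5% |
| 0.10 | 6% | 8% | 9% | 5% |
| 0.15 | 7% | 12% | 14% | 5% |
| 0.30 | 15% | 35% | 45% | 5% |
| 0.45 | 28% | 69% | 81% | 5% |

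The (β1, β3) test has noncentrality zero whatever the shared gain, because it compares the arms at both visits and a common time trend cancels.

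**4. Sensitivity at d = 0.30** (codings in the order 1/2, 0/1, ±0.5).

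- ρ from 0.5 to 0.7: 14–16%, 30–43%, 37–57%.
- SD from 2.0 down to 1.4: 12–20%, 27–50%, 34–62%.
- Month 6 data on 42 of 56 per arm: 13%, 29%, 36%.
- Month 6 data on 28 of 56 per arm: 11%, 22%, 27%.

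The last two lines matter because participants entering after 10/1/2023 have only month 0 and month 3 assessments for most measures. The documents do not give their number, so 42 and 28 are assumptions.

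**The case for a change.** The best case for acting is that the slip sits in the defining sentence of the primary test, that the correction costs one character, and that a programmer working from symbols could be misled without any warning from the degrees of freedom. The same model form also serves the secondary outcomes, so one error could spread. A misread subscript in the PDF text cannot be fully excluded, but the equation and the label are both legible and nothing suggests one.

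The mismatch stands, and so does the arithmetic for literal coding. What does not stand is the step from there to a risk for the trial. To build the wrong test, an analyst would have to pass over the two terms named immediately before the parenthesis, ignore the stated purpose that follows it, and accept a test of the intervention that contains a pure time term. Nothing in the documents suggests that would happen. The larger rates also need a sizeable late gain, for which no document gives a figure. The parent analysis plan itself expects function to change quickly at first and then level off, which points to the smaller gains in the table.

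**Conclusion.** This is a clerical slip, and it calls for no change to the plan. The label should be read as β1 and β3. The sentence that carries it, the aim stated for the modelling and the supplemental plan all settle that reading. The test as described keeps its 5% error rate under every group coding, and no hypothesis, sample size, power figure or alpha depends on the subscript.

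The inflation from literal coding runs from almost nothing (5–6% at a shared gain of 0.05) to large (28–81% at 0.45). It rests on group coding, between-visit correlation, per-visit SD, shared late gain and the share of participants with month 6 data, none of which the documents give for this purpose. It should not be quoted as the trial's false-positive risk. This conclusion covers the label only and says nothing about the rest of the test specification.
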